The latest ACCP international guidelines suggest an indefinite duration of anticoagulation in all patients after an unprovoked event, provided they are at low or moderate risk of bleeding ³. However, the rate of fatal bleeding while on indefinite treatment is comparable to that of fatal PE in patients in whom anticoagulation is discontinued ⁴, and the case-fatality rate of major bleeding is higher than that of symptomatic recurrent events ⁵. It should also be pointed-out that the ACCP guidelines propose a score to assess the individual bleeding risk which evaluates as at high bleeding risk subjects aged > 75 years. All these evaluations stem from studies in whom vitamin K antagonists (VKA) had been used for the secondary prevention of VTE disorders. Accordingly, most physicians do not accomplish these recommendations ⁶. In clinical practice, prolonging indefinitely anticoagulation beyond the first months appears a reasonable choice only in some categories of patients, including those with a personal or familiar history of VTE, those with known major thrombophilic disorders (such as deficiencies in the natural anticoagulants or the antiphospholipid syndrome), those with severe presentations (such as life-threatening PE) and those with a cava filter.

New scenarios have recently been offered by the use of the novel direct oral anticoagulants (DOACs), both for initial and standard anticoagulation course and for extended treatment. In particular for the last clinical scope, low-dose apixaban (2.5 mg BID) ⁷, aspirin (100 mg OD) ⁸, and sulodexide (500 mg BID) ⁹, proved effective (though with different extent) and with better safety results than expected by using VKAs. Indeed, randomized placebo-controlled clinical trials conducted in patients with unprovoked VTE who had received 3-12 months of conventional anticoagulation showed a reduction of the incidence of recurrent events of approximately 80% with low-dose apixaban ⁷, 35% with aspirin ⁸ and 50% with sulodexide ⁹, respectively.

Finally, in the DULCIS management study ¹⁰ it was shown that in patients with an unprovoked (or associated with a weak risk factor) symptomatic episode of proximal DVT and/or PE who had received a standard course of anticoagulation with VKA, serial D-dimer measurement in combination with the assessment of residual thrombosis in the deep leg veins is suitable in clinical practice to

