2) D-DIMER ASSESSMENT

Patients included in both Subgroups of the study are invited to undergo D-dimer measurements. They are informed that:

- a) the cut-off value used in the study can be different than the limit values shown in the laboratory reports of the tests;
- b) in case D-dimer assay would give a positive result (above the study cut-off value established for the used assay) they would be advised to continue anticoagulation or, if anticoagulation has already been stopped, to resume anticoagulant treatment by assuming in both cases the novel direct oral anticoagulant drug apixaban (Eliquis) 2.5 mg BID, provided by the study, that is associated with a low risk of bleeding, according to the currently available scientific literature. The patients will then receive a serial determination of D-dimer assay (a maximum of four determinations in case of negative results) by using the routinely locally adopted method assay (provided it is one of those listed in Appendix 1).

The D-dimer measurement should be performed at the moment of patient screening, when patients still assume their anticoagulant treatment (T0), and at 15±2 days (T1), 30±4 days (T2), and 60±5 (T3) days after their anticoagulant treatment has been stopped.

Patients with a positive D-dimer assay who may refuse to continue anticoagulation will be followed for the next 18 months.

Patients with positive D-dimer results at T0 (see Appendix 1 for D-dimer cut-off levels according sex) are offered to continue anticoagulant treatment by shifting to receive apixaban (Eliquis) 2.5 mg BID. If they accept to be treated with apixaban they are included in the study and followed-up for 18 months; if they decide to continue their current anticoagulant treatment (different than apixaban 2.5 mg BID) they are excluded from further participation in the study. Patients with negative D-dimer result at T0 are invited to stop assuming their anticoagulant therapy and continue on serial D-dimer measurements. At the first positive D-dimer result in serial testing, they are invited to resume anticoagulation by assuming apixaban (Eliquis) 2.5 mg BID.

Patients with persistently negative results of the four serial D-dimer measurements, are invited to stay definitively without anticoagulation and discouraged from resuming any antithrombotic drug for secondary VTE prevention.

3) RESUMING ANTICOAGULATION: APIXABAN

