Targeted Physical Examination	X				X	
Vital Signs	X					
Assessment of Signs and Symptoms	X				X	
Compression Ultrasound Doppler (CUS) evaluation	X					
Echocardiography evaluation	X					
Pregnancy test	X					
D-Dimer Test	X	X				
Follow up every 3-6 Months until 18 months		X	X	X		
Clinical Drug Supplies						
Dispense Study Treatment			X			From the first

Procedure	Screening Visit (T0)	D-Dimer test T1, T2, T3			Last Visit	Notes
		Patient with negative D-Dimer	Patient with positive D-Dimer	Patient with positive D-Dimer who refuse Apixaban		
						positive D-Dimer test Apixaban will be dispensed every 6 months
Efficacy End Points						
Primary		X	X	X	X	
Secondary		X	X	X	X	
Safety End Points						
Primary		X	X	X	X	
Secondary		X	X	X	X	

STATISTICAL CONSIDERATIONS

The aim of this management study is to demonstrate that in patients with a first unprovoked VTE a combination of a prediction rule based on D-dimer and low-dose DOAC in those at higher recurrence risk result in a recurrence risk comparable to the population of patients with provoked VTE.

Assumptions

based on the results of the DULCIS study¹⁰, approximately 45% of all eligible patients are expected to discontinue anticoagulation, with an annual rate of recurrent VTE events around 3% (95% 2.0 to 4.4%).

In the remaining 55% of patients who will be encouraged to use apixaban, based on the results of the Amplify Extension study the expected rate of recurrent VTE is around 1.7% after the first year of treatment.

Based on the metanalysis¹² the annual recurrence risk in patients with provoked VTE is 3.3%

Based on these assumptions, we expect the recurrence rate at 12 months to be:

$$0.45*0.03+0.55*0.017=2.2\%$$

Sample size: With an expected annual recurrence rate of 2.2% in the APIDULCIS population, we calculated the sample size to demonstrate, with an 80% power, that the 95% CI is below 3.5% according to Shen¹². The required sample size is 1148 patients to be recruited for the purpose of the APIDULCIS study.

Kaplan–Meier survival curves will be plotted to estimate the cumulative incidence of symptomatic recurrent VTE; hazard ratios (HR) and their 95% confidence intervals (CI) will be calculated for subgroup analyses.

Safety end-points and interim analysis

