D-dimer should be measured at the following time points after anticoagulation is stopped.

T0 = during anticoagulation

T1 = 15±2 days after anticoagulation is stopped

T2 = 30±4 days after anticoagulation is stopped

T3 = 60±5 days after anticoagulation is stopped

PREDEFINED CUT-OFF LEVELS FOR NEGATIVE/POSITIVE

D-dimer cut-off levels (ng/ml) for males and females (aged 18-75 years)

	Males	Females
Methods with results in FEU		
- VIDAS D-Dimer (bioMerieux)	350 ng/mL	500 ng/mL
- Innovance D-dimer (Siemens)	0.35 mg/L	0.50 mg/L
- Sta Liatest D-Di (Diagnostica Stago)	0.35 µg/mL	0.50 µg/mL
- HemosIL D-Ddimer HS 500 (Werfen)	350 ng/mL	500 ng/mL
- HemosIL D-Dimer HS (Werfen)	350 ng/mL	500 ng/mL
- AcuStar D-Dimer (Werfen)	350 ng/mL	500 ng/mL
Methods with values in DDU		
- HemosIL D-Dimer HS (Werfen)	175 ng/mL	250 ng/mL
- HemosIL D-Dimer (Werfen)	175 ng/mL	250 ng/mL
- Sclavo Auto D-dimer (Dasit)	175 ng/mL	250 ng/mL

APPENDIX 2

OUTCOME DEFINITIONS

VENOUS THROMBOEMBOLISM (VTE)

Pulmonary embolism (PE)

Symptoms of PE with one of the following findings.

- A new intraluminal filling defect in (sub) segmental or more-proximal branches on spiral computed tomography (CT) of the chest.
- A new intraluminal filling defect, or an extension of an existing defect, or a new sudden cutoff of vessels more than 2.5 mm in diameter on the pulmonary angiogram.
- A new perfusion defect of at least 75% of a segment, with a local normal ventilation result (high probability) on ventilation/perfusion lung scintigraphy (VQ scan).
- Inconclusive spiral CT, pulmonary angiography, or VQ scan evidence of a new or recurrent PE, with demonstration of a new or recurrent deep vein thrombosis (DVT) in the lower extremities by compression ultrasound (CUS) or venography.

Proximal deep vein thrombosis (DVT)

Symptoms of DVT with one of the following findings.

(a) For a NEW DVT: abnormal CUS, or an intraluminal filling defect on venography.

(b) For a RECURRENT DVT:

- abnormal CUS where compression had been normal or, if non-compressible during screening, a substantial increase (4 mm or more) in diameter of the thrombus during full compression, or
- an extension of an intraluminal filling defect, or a new intraluminal filling defect, or an extension of non-visualization of veins in the presence of a sudden cut-off on venography.

DEATH

For all patients who died during the study, the cause of death was adjudicated to one of the following categories.

- VTE-related death

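### The 2.2% planning rate leaves out the 15 to 60 untreated days that late D-dimer converters spend off drug; power at 1148 is lower than stated, by an amount the protocol does not fix

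*Protocol*

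**What the plan says.** Statistical Considerations builds the planning rate from two groups. In the first, "approximately 45% of all eligible patients are expected to discontinue anticoagulation", "with an annual rate of recurrent VTE events around 3" per cent. The second is introduced with "In the remaining 55% of patients who will be encouraged to use apixaban", and for it "the expected rate of recurrent VTE is around 1.7% after the first year of treatment". The blend, 0.45 × 0.03 + 0.55 × 0.017, is printed as 2.2%. The sample size of 1148 is then set to show "with an 80% power, that the 95% CI is below 3.5" per cent. The synopsis repeats the formula and the 2.2%.

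The section on D-dimer assessment describes who is treated and when. Patients positive at T0 are offered an immediate switch to apixaban. Patients negative at T0 stop their anticoagulant and are retested. "At the first positive D-dimer result in serial testing, they are invited to resume anticoagulation by assuming apixaban (Eliquis) 2.5 mg BID". Appendix 1 sets the tests at 15±2 and 30±4 days, and the last one as "T3 = 60±5 days after anticoagulation is stopped".

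Under Follow-up and Study End-points, follow-up runs from recruitment and the primary efficacy end-point counts events in all included patients. Under Study Assessments and Procedures, patients are enrolled at the screening visit, before the serial tests.

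**The concern.** The 1.7% is an on-treatment rate. A patient who converts at T1 to T3 has no treatment for 13 to 65 days once the visit windows are included, and those days lie inside the follow-up that counts. The protocol regards D-dimer-positive patients as the high-risk group, yet the formula gives their untreated time the treated rate. The gap comes from the algorithm and exists even if every patient accepts apixaban, so it is a separate matter from refusal.

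What is at stake is the power statement. The criterion leaves a margin of only a few events, so a small rise in the true rate costs several points of power.

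**Working it through.** **Reproducing the printed figure.** The protocol does not say whether the 95% limit is one- or two-sided. With a one-sided exact (Clopper-Pearson) 95% upper limit below 3.5%, success at n = 1148 means at most 29 events: the limit is 3.43% at 29 events and 3.53% at 30. Expected events are 1148 × 0.022 = 25.3. The binomial probability of 29 or fewer events at 2.2% is 80.6%, which matches the printed 80%. A two-sided exact limit gives 68.3%, so the one-sided rule is used below.

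**Inputs.**
- From the protocol: 45%, 55%, 3%, 1.7%, and test times of 15, 30 and 60 days.
- Assumed, because the protocol gives neither: f, the share of positives found at T1 to T3, taken as 0.10 to 0.75; and d, their mean days off drug, taken as 15 to 35. An equal split over T1 to T3 gives (15 + 30 + 60)/3 = 35.
- Off-drug annual rate u, also not given. Values tried:
  - 3%, the rate for patients who stop;
  - 5%, an intermediate assumption;
  - 6.9%, from the Background's 50% at 10 years at constant hazard: 1 − 0.5^(1/10) = 6.7% as a yearly risk, or ln 2/10 = 6.9% as a rate;
  - 8.5%, from the Background's "a reduction of the incidence of recurrent events of approximately 80% with low-dose apixaban": 1.7%/(1 − 0.80).

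**Formula.** Addition to the pooled rate = 0.55 × f × (d/365) × (u − 1.7%). It is positive whenever u exceeds 1.7%. Example with f = 0.50, d = 35, u = 8.5%: 0.55 × 0.50 × 0.0959 × 6.8% = 0.179 points, so 2.2% becomes 2.38%, or 1148 × 0.00179 = 2.1 extra events.

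**Results, starting from the printed 2.2%** (at most 29 events at 1148, at most 31 at 1,200):

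| u per year | f | d | Addition (points) | Extra events at 1148 | Power at 1148 | Power at 1,200 |
|---|---|---|---|---|---|---|
| none | – | – | 0 | 0 | 80.6% | 84.3% |
| 3% | 0.50 | 35 | 0.034 | 0.4 | 78.3% | 82.2% |
| 5% | 0.50 | 15 | 0.037 | 0.4 | 78.1% | 82.0% |
| 5% | 0.50 | 35 | 0.087 | 1.0 | 74.5% | 78.7% |
| 6.9% | 0.50 | 35 | 0.137 | 1.6 | 70.7% | 75.1% |
| 8.5% | 0.10 | 35 | 0.036 | 0.4 | 78.2% | 82.1% |
| 8.5% | 0.25 | 15 | 0.038 | 0.4 | 78.0% | 81.9% |
| 8.5% | 0.25 | 35 | 0.090 | 1.0 | 74.3% | 78.5% |
| 8.5% | 0.50 | 15 | 0.077 | 0.9 | 75.3% | 79.4% |
| 8.5% | 0.50 | 35 | 0.179 | 2.1 | 67.3% | 71.9% |
| 8.5% | 0.75 | 35 | 0.269 | 3.1 | 59.8% | 64.6% |

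Over the full grid (f = 0.10, 0.25, 0.50, 0.75; d = 15, 35), power at 1148 runs from 77.1 to 80.4% at 3% per year, 71.2 to 80.1% at 5%, and 59.8 to 79.6% at 8.5%. One extra event lowers power from 80.6% to 74.5%.

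**Expected recurrences.** The printed 38 is 1150 × 0.022 × 1.5 = 37.95. The gap occurs once, early in follow-up, so it adds 1150 × 0.00179 = 2.1 in the f = 0.50, d = 35, u = 8.5% case, giving about 40.

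**Interaction with rounding.** The blend as printed sums to 2.285%, not 2.2%. That is a separate matter and alone gives 74.7% power at 1148. With f = 0.50, d = 35 and u = 8.5% added, power is 60.2%.

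**The case against.** The strongest reply concerns size. None of f, d and u is in the protocol, and over the values tried the loss runs from under 1 point to about 20. The 8.5% combines the 1.7% with a relative reduction from placebo-controlled trials after 3 to 12 months of anticoagulation. This cohort has had 12 to 18 months, and its late converters have already tested negative at least once. This stands, and it is why only a range can be given.

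The group accounting is also loose. A patient who recurs on day 20 with a negative T0 and T1 has not yet been classed as positive. Whether the earlier management study's 3% already contains such events depends on how that study started its clock and assigned patients, which the protocol does not say. If it does contain some, the addition shrinks. This stands too and must be checked before the correction is applied.

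The inputs are openly rough. The printed interval of 2.0 to 4.4% around the 3% moves the blend from 1.84% to 2.92% and power at 1148 from 96% to 25%, far more than the gap does. That puts the effect in proportion. But the interval is uncertainty in both directions, whereas the gap pushes in one direction only.

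The synopsis sets an accrual goal of 1,200, where the milder cases stay near or above 80%. It also says that hypothesis testing is unnecessary and cites around 800 subjects, so the 80% power claim appears only in the main text. The slack is real but does not cover f = 0.50, d = 35 at 8.5%. The synopsis uses the same 2.2% for its precision statement and its 38 recurrences.

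A reader might infer that the study is shown to be badly underpowered. The documents do not support that: at the mild end of the grid power still rounds to 80%.

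**Conclusion.** The planning rate omits off-drug time that the design itself creates. As the formula is written, the omission lowers the pooled rate and raises the stated power whenever late converters recur off drug at more than 1.7% per year. For f = 0.10 to 0.75 and d = 15 to 35, power at 1148 is 77 to 80% at 3% per year off drug, 71 to 80% at 5%, and 60 to 80% at 8.5%, against 80.6% without the gap. At 1,200, the f = 0.50, d = 35, u = 8.5% case gives 71.9%.

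These figures rest on a one-sided exact limit, inferred because it comes closest to reproducing 1148; on full uptake of apixaban; on assumed f, d and u; and on gap events not already being counted in the 3%. The finding concerns the planning calculation only. It does not show that the treatment algorithm is wrong or that more patients must be enrolled.

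**What to change.** In Assumptions and in the synopsis, replace the flat 0.55 × 1.7% with a time-weighted term:

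0.55 × [(1 − f × d/365) × 1.7% + (f × d/365) × off-drug rate]

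Take f and d by test time from the earlier management study that already supplies the 45% and the 3%, or show a range if they cannot be obtained. First check whether that study's 3% already includes recurrences before a positive test, so that they are not counted twice. Then restate the pooled rate, the expected recurrences, and the power at 1148 and at 1,200 as a range in place of an unqualified 80%, and say whether the 95% limit is one- or two-sided.

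The cost is one recalculation, a wording change and a less favourable stated power. The treatment algorithm and the enrolment target do not change.

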 - ✓ current or recent gastrointestinal ulceration, presence of malignant neoplasms at high risk of bleeding, recent brain or spinal injury, recent brain, spinal or ophthalmic surgery, recent intracranial hemorrhage, known or suspected esophageal varices, arteriovenous malformations, vascular aneurysms or major intra-spinal or intracerebral vascular abnormalities;
 - ✓ concomitant treatment with any other anticoagulant agent e.g., unfractionated heparin (UFH), low molecular weight heparins, heparin derivatives (fondaparinux, etc.), oral anticoagulants (warfarin, rivaroxaban, dabigatran, etc.) except under specific circumstances of switching anticoagulant therapy or when UFH is given at doses necessary to maintain an open central venous or arterial catheter.

The patients with one of the absolute contraindications to Eliquis are invited to resume anticoagulation using a different anticoagulant drug.

FOLLOW-UP AND STUDY END-POINTS

All patients included in the study, a) those with persistently negative D-dimer who stopped anticoagulation, b) those with positive D-dimer who continued or resumed anticoagulant treatment by assuming apixaban 2.5 mg BID, and c) those with positive D-dimer who may refuse to assume apixaban as well as any other anticoagulant or antithrombotic agent for secondary VTE prevention, will be followed up for at least 18 months after recruitment in the study. They will be examined or interviewed telephonically every 3-6 months in order to assess their health conditions and to check the occurrence of events. All primary events occurring during the follow-up, including objectively proven recurrent VTE, major or clinically relevant non-major bleedings and deaths from any cause will be objectively documented according to widely accepted guidelines and recorded. All the events will be adjudicated by a central adjudication committee. All the patients are invited to immediately refer to the enrolling center at the appearance of signs or symptoms compatible with venous thromboembolism or other complications (such as bleeding episodes).

Primary efficacy end-point: the composite of confirmed recurrent VTE and VTE-related death occurring during follow-up in all included patients

Primary safety end-point: major bleeding ¹¹ complications occurring during the follow-up period in all included patients

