Secondary efficacy end-points: other thromboembolic events, (severe) post-thrombotic syndrome (at the end of follow-up period patients with DVT as index event should receive a final evaluation of the Villalta score),

Secondary safety end-points: clinically relevant non major bleeding complications, overall mortality

All suspected outcome events and deaths will be evaluated by a central adjudication committee whose members will be unaware of patient name, D-dimer testing results, type of management or enrolling center.

STUDY ASSESSMENTS AND PROCEDURES

This study is divided into 2 main periods:

1. Screening: After obtaining written informed consent, all potential patients will complete the screening visit. If fulfilling the eligibility assessments, they will be enrolled. Evaluation of results of D-dimer laboratory results, if the value is positive the patients are invited to continue anticoagulant treatment by assuming Apixban 2,5 mg BID for 18 months. Patients with negative value stop the must anticoagulation and will repeat the D-dimer test 15±2 days later.

Pregnancy is highly discouraged in these patients and if programmed patients are excluded from the study. If sexually active, be practicing an effective method of birth

control (e.g., intrauterine device, double---barrier method) before entry and throughout the study. A pregnancy test is mandatory before enrollment.

2. Course of the study: Every three-six months, a physical examination or a phone call will be made to assess compliance to treatment, health status and the occurrence of events.

The follow up will be performed until the completion of the study for these kinds of patients:

- those with persistently negative D-dimer who stopped anticoagulation,
- those with positive D-dimer who continued or resumed anticoagulant treatment by assuming apixaban 2.5 mg BID, and
- those with positive D-dimer who may refuse to assume apixaban as well as any other anticoagulant or antithrombotic agent for secondary VTE prevention, will be followed up for at least 18 months after recruitment in the study.
- those who had premature discontinuation.

Procedure	Screening Visit (T0)	D-Dimer test T1, T2, T3			Last Visit	Notes
		Patient with negative D-Dimer	Patient with positive D-Dimer	Patient with positive D-Dimer who refuse Apixaban		
Eligibility Assessments						
Informed Consent	X					
Inclusion/Exclusion Criteria	X					
Medical History	X					
Safety Assessments						
Physical Examination	X				X	

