Based on a 2.2% annual event rate, a total sample size around 1150 patients and 18 months of follow-up, we expect around 38 recurrences and 2 major bleeding in our study. Since low-dose apixaban may be considered as the treatment gold-standard at the time of release of the study protocol, we plan an interim analysis when 20 primary endpoints are registered. The study will be interrupted if the relative risk of primary endpoints (HR) in the observational non-treatment arm will be >3 HR, with a p value <0.0001.

PROTOCOL SYNOPSIS

Title:	APIDULCIS: Extended anticoagulation with low-dose apixaban after a standard course anticoagulation in patients with a first venous thromboembolism who have positive D-dimer
Country:	Italy
Number of Sites:	53 centers
Research Hypothesis:	
The cumulative incidence of VTE recurrence 10 years after stopping anticoagulation is about 50% and 20% after a first unprovoked and provoked event respectively. It is not related to the duration of anticoagulant treatment. In addition, the rate of fatal bleeding on indefinite treatment is comparable to that of fatal PE in patients with anticoagulation discontinuation, and the case-fatality rate of major bleeding is higher than that of symptomatic recurrent events
 
The latest ACCP international guidelines suggest an indefinite duration of anticoagulation in all patients after an unprovoked event, at low or moderate risk of bleeding. All the available evaluations derive from studies on vitamin K antagonists (VKA) treatment. The use of the novel direct oral anticoagulants (DOACs) offers a valid alternative to vitamin k antagonist and in particular, for the extended treatment, low-dose apixaban (2.5 mg BID) proved effective with better safety results than VKA.
 
The DULCIS management study showed that in VKA patients with an unprovoked (or associated with a weak risk factor) symptomatic episode of proximal DVT, serial D-dimer measurement with the assessment of residual thrombosis allows to detect those VTE patients at low recurrence risk (annual rate, 3.0%) who can discontinue anticoagulation.
 
The latest ACCP guidelines suggest the use of D-dimer assessment after stop anticoagulation to decide the extended treatment.

Study Schema: Drugs / Doses / Length of Treatment)	Apixaban 2.5mg Treatment: 18 months

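### The stated 80% power belongs to a 12-month proportion, while the primary composite runs over all follow-up, and no planned estimate states the scale on which the 3.5% bound is judged

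*Protocol*

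**What the plan says.** Five places in the protocol bear on this.

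- **End-point** (Follow-up and Study End-points): "Primary efficacy end-point: the composite of confirmed recurrent VTE and VTE-related death occurring during follow-up in all included patients". No time point is set.
- **Sizing** (Statistical Considerations). Under Assumptions: "we expect the recurrence rate at 12 months to be" 0.45 × 0.03 + 0.55 × 0.017, printed as 2.2%. The comparator is an annual 3.3% for provoked VTE. The Sample size paragraph then calls 2.2% an annual rate and says "we calculated the sample size to demonstrate, with an 80% power, that the 95% CI is below 3.5" per cent, giving 1148 patients. The sizing method, as titled in the reference list, concerns the upper confidence limit for a binomial end-point.
- **Planned estimate** (Statistical Considerations, repeated in the Synopsis): Kaplan-Meier curves to "estimate the cumulative incidence of symptomatic recurrent VTE". VTE-related death is not mentioned.
- **Expected events**: "Based on a 2.2% annual event rate, a total sample size around 1150 patients and 18 months of follow-up, we expect around 38 recurrences" (stated under Safety end-points and interim analysis).
- **Synopsis, Statistics row**: a sufficiently precise rate estimate is enough, no hypothesis test is needed, and about 800 subjects put the upper 95% limit below 0.035 if 0.022 is observed. No time basis is given.

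The length of follow-up also varies. Patients "will be followed up for at least 18 months after recruitment in the study" (Follow-up and Study End-points, and again in Study Assessments and Procedures). Study Assessments and Procedures also says "The follow up will be performed until the completion of the study for these kinds of patients". The schedule table has "Follow up every 3-6 Months until 18 months". Study Timelines gives 18 months as the maximum per patient.

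**The concern.** The protocol fixes a bound, a power, an end-point window and an expected event count, but on two time bases. The bound and the power are 12-month or annual. The end-point and the event count cover 18 months or more. No sentence connects them, and the one named survival estimate covers only part of the composite.

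The stated 80% is therefore the power of a quantity other than the end-point as defined. If the 12-month proportion is the one judged, events in months 13 to 18 are primary events by definition but do not enter the comparison with 3.5%. If an annual rate over all follow-up is judged, they do enter, and the power is higher than stated. This choice should be in the protocol before data are seen.

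**Working it through.** **Inputs from the protocol.** n = 1148; expected 2.2% per year (unrounded: 0.0135 + 0.00935 = 2.285%); bound 3.5%; 95% confidence, sidedness not stated; about 1150 patients and 18 months for the event count. The person-year figures assume a constant rate. The protocol's 38 events rest on the same proportional scaling.

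**1. Reproduce the 1148.** Treat 12-month recurrence as binomial, find the largest event count whose upper limit is below 3.5%, and take the chance of that count or fewer.

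- One-sided 95% exact limit, or two-sided 95% Wald limit: at most 29 events. P(X ≤ 29 | 1148, 0.022) = 80.6%, which matches the stated 80%.
- Two-sided 95% exact limit: at most 27 events. P(X ≤ 27 | 1148, 0.022) = 68.3%.

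**2. Reproduce the 38.** 1150 × 0.022 × 1.5 = 37.95. This is an 18-month count.

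**3. Events outside the 12-month quantity.** 1150 × 0.022 × 0.5 = 12.65, and 12.65 / 37.95 = 33%.

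**4. Power of an annual rate over all follow-up.** Person-years: 1148 × 1.5 = 1722. Expected events at 2.2%: 0.022 × 1722 = 37.9. The exact Poisson upper limit is below 3.5 per 100 person-years for at most 45 events (two-sided) or 47 events (one-sided).

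| n = 1148, bound 3.5% | Two-sided exact | One-sided exact |
|---|---|---|
| 12-month proportion, 2.2% | 68% | 81% |
| 12-month proportion, 2.285% | 61% | 75% |
| Person-year rate, 2.2%/yr | 89% | 94% |
| Person-year rate, 2.285%/yr | 84% | 90% |
| Person-year rate, 2.2%/yr, 10% of person-time lost (assumed; 1550 person-years) | 82% | 89% |
| Person-year rate, 2.285%/yr, 10% lost (assumed) | 76% | 85% |

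**5. Is the extra power bought with a looser error rate?** If the true rate is exactly 3.5%, the person-year criterion passes with probability 2.5% (two-sided) or 4.6% (one-sided). The 12-month exact criterion passes with probability 1.7% or 3.8%. All are at or below nominal. The gain comes from the additional events.

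**6. What a person-year average can hide.** As an illustration, 3.5% per year in year 1 and 2.0% per year in months 13 to 18 average (3.5 × 1 + 2.0 × 0.5) / 1.5 = 3.0 per 100 person-years, half a point below the first-year rate.

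**The case against.** The strongest reply is that the passages can be read together. The Sample size paragraph calls 2.2% an annual rate, the comparator is annual, the event count multiplies that rate by 18 months, and the end-point counts events during follow-up. An annual rate estimated over all follow-up fits all of this, and on that reading the stated 80% is conservative. This stands, and it is why the fix adopts that reading. It does not explain the 80%, which comes from a 12-month binomial calculation, and the protocol does not name a person-year estimate.

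It can also be said that time point, interval method and sidedness are ordinary SAP content, and the SAP is not at hand. That is fair for the detail taken alone. The difference between the sizing quantity and the end-point window, and the missing death component in the Kaplan-Meier sentence, are in the protocol text.

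A 12-month estimate is also defensible. The 2.2% is derived as a 12-month figure, and a landmark leaves out later events by design. If it is chosen as primary, the protocol should say so.

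Three stronger inferences are not supported:

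- **That true power is 68%.** This needs a two-sided exact limit at 12 months, which the protocol does not specify. It reflects the interval method, not the time scale.
- **That the plan's own expected result would fail.** Set against 3.5%, 38/1150 = 3.30% has an exact 95% interval of 2.35% to 4.51%. No passage applies the bound to 18-month incidence, and the bound is annual in context. On the annual scale, 38/1725 person-years = 2.20 per 100 (1.56 to 3.02) and passes.
- **That the criterion has no link to the end-point.** The annual-rate reading supplies one. It is simply not written down.

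**Conclusion.** The point holds as a mismatch that should be fixed. The 80% power reproduces as a 12-month proportion with a one-sided exact or two-sided Wald limit, and that quantity omits about a third of the expected primary events. The end-point is defined over all follow-up, the Kaplan-Meier estimate has no time point and omits VTE-related death, and the Synopsis's precision statement has no time basis either.

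This does not show an underpowered trial. With 1722 person-years, a constant rate and exact Poisson limits, power is 89% or 94% (two-sided or one-sided) at 2.2% per year, and 84% or 90% at 2.285%. An assumed 10% loss of person-time lowers the two-sided figures to 82% and 76%. The differing follow-up statements are a smaller defect that leaves the end-point window unclear.

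**What to change.** 1. State that 3.5% is an annual bound. State that the primary estimate set against it is first composite events (recurrent VTE or VTE-related death) per 100 person-years over all follow-up.
2. Name the interval method and sidedness, for example a two-sided 95% exact Poisson interval, and restate the power for it: 89% at 2.2% per year and 84% at 2.285%, or 94% and 90% if one-sided.
3. Name the full composite in the Kaplan-Meier sentence and report its 12-month incidence alongside, as a guard against early clustering. If the 12-month estimate is made primary instead, state its power for the named interval: 81% with a one-sided exact or two-sided Wald limit, 68% with a two-sided exact limit.
4. Align the Synopsis precision statement (about 800 subjects, no test) with the Sample size paragraph (1148, 80% power), and give it a time basis.
5. Reconcile the follow-up wording across Follow-up and Study End-points, Study Assessments and Procedures, the schedule table and Study Timelines.

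The cost is a few sentences and a restated power figure. No new patients, visits or data are needed.
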